### Specific Immune-Mediated Reactions

| Adverse Events   | Severity Grade of the Event (NCI CTCAE version 4.03)  | Dose Modifications                                  | Toxicity Management   |
|--|---|---|---|
| Pneumonitis/Interstitial Lung Disease (ILD)  | Any Grade   | General Guidance                                    | For Any Grade:   |
| Grade 1
(asymptomatic, clinical or diagnostic observations only; intervention not indicated) | No dose modifications required. However, consider holding study drug/study regimen dose as clinically appropriate and during diagnostic work-up for other etiologies.   | For Grade 1 (radiographic changes only):     | 
 
– Monitor and closely follow up in 2 to 4 days for clinical symptoms, pulse oximetry (resting and exertion), and laboratory work-up and then as clinically indicated.
 
– Consider Pulmonary and Infectious disease consult.
 
   |
| Grade 2
(symptomatic; medical intervention indicated; limiting instrumental ADL)             | Hold study drug/study regimen dose until Grade 2 resolution to Grade $\leq 1$ . 
 
• If toxicity worsens, then treat as Grade 3 or Grade 4.
 
• If toxicity improves to Grade <math>\leq 1</math>, then the decision to reinstitute study drug/study regimen will be based upon treating physician's clinical judgment and after completion of steroid taper.
 
 | For Grade 2 (mild to moderate new symptoms): | 
 
– Monitor symptoms daily and consider hospitalization.
 
– Promptly start systemic steroids (e.g., prednisone 1 to 2 mg/kg/day PO or IV equivalent).
 
– Reimage as clinically indicated.
 
– If no improvement within 3 to 5 days, additional workup should be considered and prompt treatment with IV methylprednisolone 2 to 4 mg/kg/day started
 
– If still no improvement within 3 to 5 days despite IV methylprednisolone at 2 to 4 mg/kg/day, promptly start immunosuppressive therapy such as TNF inhibitors (e.g., infliximab at 5 mg/kg every 2 weeks). Caution: It is important to rule out sepsis and refer to infliximab label for general guidance before using infliximab.
 
– Once the patient is improving, gradually taper steroids over <math>\geq 28</math> days and consider prophylactic antibiotics, antifungals, or
 
 |

|   |   |  |  |
|---|---|--|--|
|   |   |  | anti-PJP treatment (refer to current NCCN guidelines for treatment of cancer-related infections [Category 2B recommendation]) a 
 
– Consider pulmonary and infectious disease consult.
 
– Consider, as necessary, discussing with study physician.
 
  |
| Grade 3 or 4

(Grade 3: severe symptoms; limiting self-care ADL; oxygen indicated)

(Grade 4: life-threatening respiratory compromise; urgent intervention indicated [e.g., tracheostomy or intubation]) | Permanently discontinue study drug/study regimen. | For Grade 3 or 4 (severe or new symptoms, new/worsening hypoxia, life-threatening): | 
 
– Promptly initiate empiric IV methylprednisolone 1 to 4 mg/kg/day or equivalent.
 
– Obtain Pulmonary and Infectious disease consult; consider, as necessary, discussing with study physician.
 
– Hospitalize the patient.
 
– Supportive care (e.g., oxygen).
 
– If no improvement within 3 to 5 days, additional workup should be considered and prompt treatment with additional immunosuppressive therapy such as TNF inhibitors (e.g., infliximab at 5 mg/kg every 2 weeks' dose) started. Caution: rule out sepsis and refer to infliximab label for general guidance before using infliximab.
 
– Once the patient is improving, gradually taper steroids over <math>\geq 28</math> days and consider prophylactic antibiotics, antifungals, and, in particular, anti-PJP treatment (refer to current NCCN guidelines for treatment of cancer-related infections [Category 2B recommendation]).a
 
 |
| Diarrhea/Colitis   | Any Grade                                  | General Guidance  | For Any Grade: 
 
– Monitor for symptoms that may be related to diarrhea/enterocolitis (abdominal pain, cramping, or changes in bowel habits such as increased frequency over baseline or blood in stool) or related to bowel perforation (such as sepsis, peritoneal signs, and ileus).
 
– Patients should be thoroughly evaluated to rule out any alternative etiology (e.g., disease progression, other medications, or infections), including testing for clostridium difficile toxin, etc.
 
– Steroids should be considered in the absence of clear alternative etiology, even for low-grade events, in order to prevent potential progression to higher grade event.
 
   |

|  |   |   |
|--|---|---|
|  |   | 
 
– Use analgesics carefully; they can mask symptoms of perforation and peritonitis.
 
  |
| Grade 1

(Diarrhea: stool frequency of <4 over baseline per day)

(Colitis: asymptomatic; clinical or diagnostic observations only) | No dose modifications.  | 
For Grade 1:
 
 
– Monitor closely for worsening symptoms.
 
– Consider symptomatic treatment, including hydration, electrolyte replacement, dietary changes (e.g., American Dietetic Association colitis diet), and loperamide. Use probiotics as per treating physician's clinical judgment.
 
   |
| Grade 2

(Diarrhea: stool frequency of 4 to 6 over baseline per day)

(Colitis: abdominal pain; mucus or blood in stool)            | 
Hold study drug/study regimen until resolution to Grade <math>\leq 1</math>
 
 
• If toxicity worsens, then treat as Grade 3 or Grade 4.
 
• If toxicity improves to Grade <math>\leq 1</math>, then study drug/study regimen can be resumed after completion of steroid taper.
 
 | 
For Grade 2:
 
 
– Consider symptomatic treatment, including hydration, electrolyte replacement, dietary changes (e.g., American Dietetic Association colitis diet), and loperamide and/or budesonide.
 
– Promptly start prednisone 1 to 2 mg/kg/day PO or IV equivalent.
 
– If event is not responsive within 3 to 5 days or worsens despite prednisone at 1 to 2 mg/kg/day PO or IV equivalent, GI consult should be obtained for consideration of further workup, such as imaging and/or colonoscopy, to confirm colitis and rule out perforation, and prompt treatment with IV methylprednisolone 2 to 4 mg/kg/day started.
 
– If still no improvement within 3 to 5 days despite 2 to 4 mg/kg IV methylprednisolone, promptly start immunosuppressives such as infliximab at 5 mg/kg once every 2 weeksa. Caution: it is important to rule out bowel perforation and refer to infliximab label for general guidance before using infliximab.
 
– Consider, as necessary, discussing with study physician if no resolution to Grade <math>\leq 1</math> in 3 to 4 days.
 
– Once the patient is improving, gradually taper steroids over <math>\geq 28</math> days and consider prophylactic antibiotics, antifungals, and anti-PJP treatment (refer to current NCCN guidelines for treatment of cancer-related infections [Category 2B recommendation]).a
 
 |

|   |  |   |
|---|--|---|
| Grade 3 or 4
(Grade 3 diarrhea: stool frequency of $\geq 7$ over baseline per day;
Grade 4 diarrhea: life threatening consequences)
(Grade 3 colitis: severe abdominal pain, change in bowel habits, medi-cal intervention indicated, peritoneal signs;
Grade 4 colitis: life-threatening consequences, urgent intervention indicated) | Grade 3
Permanently discontinue study drug/study regimen for Grade 3 if toxicity does not improve to Grade $\leq 1$ within 14 days; study drug/study regimen can be resumed after completion of steroid taper.

Grade 4
Permanently discontinue study drug/study regimen.    | For Grade 3 or 4:
– Promptly initiate empiric IV methylprednisolone 2 to 4 mg/kg/day or equivalent.
– Monitor stool frequency and volume and maintain hydration.
– Urgent GI consult and imaging and/or colonoscopy as appropriate.
– If still no improvement within 3 to 5 days of IV methylprednisolone 2 to 4 mg/kg/day or equivalent, promptly start further immunosuppressives (e.g., infliximab at 5 mg/kg once every 2 weeks). Caution: Ensure GI consult to rule out bowel perforation and refer to infliximab label for general guidance before using infliximab.
– Once the patient is improving, gradually taper steroids over $\geq 28$ days and consider prophylactic antibiotics, antifungals, and anti-PJP treatment (refer to current NCCN guidelines for treatment of cancer-related infections [Category 2B recommendation]). a |
| Hepatitis (elevated LFTs)

Infliximab should not be used for management of immune-related hepatitis.   | Any Grade

General Guidance  | For Any Grade:
– Monitor and evaluate liver function test: AST, ALT, ALP, and TB.
– Evaluate for alternative etiologies (e.g., viral hepatitis, disease progression, concomitant medications).   |
| Grade 1
(AST or ALT $>$ ULN and $\leq 3.0 \times$ ULN and/or TB $>$ ULN and $\leq 1.5 \times$ ULN)  | 
 
• No dose modifications.
 
• If it worsens, then treat as Grade 2 event.
 
  | For Grade 1:
– Continue LFT monitoring per protocol.  |
| Grade 2
(AST or ALT $> 3.0 \times$ ULN and $\leq 5.0 \times$ ULN and/or TB $> 1.5 \times$ ULN and $\leq 3.0 \times$ ULN)  | 
 
• Hold study drug/study regimen dose until Grade 2 resolution to Grade <math>\leq 1</math>.
 
• If toxicity worsens, then treat as Grade 3 or Grade 4.
 
• If toxicity improves to Grade <math>\leq 1</math> or baseline, resume study
 
 | For Grade 2:
– Regular and frequent checking of LFTs (e.g., every 1 to 2 days) until elevations of these are improving or resolved.
– If no resolution to Grade $\leq 1$ in 1 to 2 days, consider, as necessary, discussing with study physician.
– If event is persistent ( $> 3$ to 5 days) or worsens, promptly start prednisone 1 to 2 mg/kg/day PO or IV equivalent.   |

|   |  |   |
|---|--|---|
|   | drug/study regimen after completion of steroid taper.  | 
 
– If still no improvement within 3 to 5 days despite 1 to 2 mg/kg/day of prednisone PO or IV equivalent, consider additional work up and start prompt treatment with IV methylprednisolone 2 to 4 mg/kg/day.
 
– If still no improvement within 3 to 5 days despite 2 to 4 mg/kg/day of IV methylprednisolone, promptly start immunosuppressives (i.e., mycophenolate mofetil).a Discuss with study physician if mycophenolate mofetil is not available. Infliximab should NOT be used.
 
– Once the patient is improving, gradually taper steroids over <math>\geq 28</math> days and consider prophylactic antibiotics, antifungals, and anti-PJP treatment (refer to current NCCN guidelines for treatment of cancer-related infections [Category 2B recommendation]).a
 
           |
| Grade 3 or 4

(Grade 3: AST or ALT $>5.0 \times$ ULN and $\leq 20.0 \times$ ULN and/or TB $>3.0 \times$ ULN and $\leq 10.0 \times$ ULN)

(Grade 4: AST or ALT $>20 \times$ ULN and/or TB $>10 \times$ ULN) | 
For Grade 3:
 
For elevations in transaminases <math>\leq 8 \times</math> ULN, or elevations in bilirubin <math>\leq 5 \times</math> ULN:
 
 
• Hold study drug/study regimen dose until resolution to Grade <math>\leq 1</math> or baseline
 
• Resume study drug/study regimen if elevations downgrade to Grade <math>\leq 1</math> or baseline within 14 days and after completion of steroid taper.
 
• Permanently discontinue study drug/study regimen if the elevations do not downgrade to Grade <math>\leq 1</math> or baseline within 14 days
 
 
For elevations in transaminases <math>>8 \times</math> ULN or elevations in bilirubin <math>>5 \times</math> ULN, discontinue study drug/study regimen.
 
Permanently discontinue study drug/study regimen for any case
 | 
For Grade 3 or 4:
 
 
– Promptly initiate empiric IV methylprednisolone at 1 to 4 mg/kg/day or equivalent.
 
– If still no improvement within 3 to 5 days despite 1 to 4 mg/kg/day methylprednisolone IV or equivalent, promptly start treatment with immunosuppressive therapy (i.e., mycophenolate mofetil). Discuss with study physician if mycophenolate is not available. Infliximab should NOT be used.
 
– Perform hepatology consult, abdominal workup, and imaging as appropriate.
 
– Once the patient is improving, gradually taper steroids over <math>\geq 28</math> days and consider prophylactic antibiotics, antifungals, and anti-PJP treatment (refer to current NCCN guidelines for treatment of cancer-related infections [Category 2B recommendation]).a
 
 |

meeting Hy's law criteria (AST and/or ALT  $>3 \times$  ULN + bilirubin  $>2 \times$  ULN without initial findings of cholestasis (i.e., elevated alkaline P04) and in the absence of any alternative cause.b

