## 6.3 Liver Function Test Abnormalities

If a patient shows an AST or ALT  $\geq 3 \times$  ULN together with total bilirubin  $\geq 2 \times$  ULN, refer to Appendix 1 for further instructions. These cases should be reported as SAEs if, after evaluation, they meet the criteria for a Hy's law case or if any of the individual liver test parameters fulfill any of the SAE criteria.

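### Appendix 1, hepatitis, Grade 3: the hold-and-resume rule and the discontinue rule overlap when transaminases and bilirubin are both Grade 3 and only one exceeds its cut-off

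*Combined protocol and SAP*

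**What the plan says.** All of this is in Appendix 1, Specific Immune-Mediated Reactions, Hepatitis (elevated LFTs), unless another place is named.

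- **Grade 3 definition.** AST or ALT >5 to 20 × ULN and/or total bilirubin >3 to 10 × ULN. Both analytes can therefore be Grade 3 together.
- **Hold rule.** It applies to transaminases ≤8 × "ULN, or elevations in bilirubin" ≤5 × ULN. Drug is held, then: "Resume study drug/study regimen if elevations downgrade to Grade" ≤1 or baseline within 14 days and once the steroid taper is complete. Otherwise: "Permanently discontinue study drug/study regimen if the elevations do not downgrade to Grade" ≤1 or baseline in that time.
- **Discontinue rule.** For transaminases >8 × ULN or bilirubin >5 × "ULN, discontinue study drug/study regimen".
- **Hy's law stop, same cell.** "Permanently discontinue study drug/study regimen for any case" with AST and/or ALT >3 × ULN plus bilirubin >2 × ULN, without initial cholestasis and without an alternative cause.
- **Grade 2 row.** AST or ALT >3 to 5 × ULN and/or bilirubin >1.5 to 3 × ULN: hold, and after recovery resume "drug/study regimen after completion of steroid taper". The Hy's law stop is not repeated here, nor in the Any Grade row, which opens with "Monitor and evaluate liver function test: AST, ALT, ALP, and TB".
- **General Considerations (Appendix 1).** Drug should be permanently discontinued for Grade 3 events with a high likelihood of morbidity or mortality, even where the tables do not list the event.
- **Section 6.3.** AST or ALT ≥3 × ULN with bilirubin ≥2 × ULN sends the reader to Appendix 1. On reporting: "These cases should be reported as SAEs if, after evaluation, they meet the criteria for a Hy's law case".

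**The concern.** The two Grade 3 rules use the same pair of cut-offs and look as if they were meant to divide Grade 3 events between them. They do not, because each is joined by 'or'. With ALT 12 and bilirubin 4 × ULN, the bilirubin branch of the hold rule applies and so does the transaminase branch of the discontinue rule. The cell does not say which prevails.

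What is at stake is re-dosing after a Grade 3 liver event, in a trial where Section 11.1.3 lists hepatitis and transaminase increases as an event of special interest. If the values recover quickly, one rule allows tremelimumab again and the other does not, so two sites could handle the same result differently.

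**Working it through.** No figure in the plan bears on this point, so the check applies the printed cut-offs as logical conditions. T is the higher of AST and ALT and B is total bilirubin, both as multiples of ULN.

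**Conditions**
- Both analytes at Grade 3: 5 < T ≤ 20 and 3 < B ≤ 10
- Hold rule: T ≤ 8 or B ≤ 5
- Discontinue rule: T > 8 or B > 5
- Hy's law laboratory limits: T > 3 and B > 2

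**Worked cases, both analytes at Grade 3**

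| T | B | Hold rule | Discontinue rule |
|---|---|---|---|
| 6 | 4 | yes | no |
| 12 | 4 | yes | yes |
| 7 | 6 | yes | yes |
| 10 | 6 | no | yes |

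The rules overlap exactly when one analyte is above its cut-off and the other is not.

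**Size of the overlap within the rule.** On a grid of 0.1 × ULN, with T from 5.1 to 20.0 (150 steps) and B from 3.1 to 10.0 (70 steps), there are 150 × 70 = 10,500 points.
- T > 8, B ≤ 5: 120 × 20 = 2,400 points, both rules
- T ≤ 8, B > 5: 30 × 50 = 1,500 points, both rules
- T ≤ 8, B ≤ 5: 30 × 20 = 600 points, hold only
- T > 8, B > 5: 120 × 50 = 6,000 points, discontinue only

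The overlap is 2,400 + 1,500 = 3,900 points, and 3,900 / 10,500 = 37%. These are areas of the rule, not shares of patients.

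**What other text settles**
1. If both analytes are Grade 3, then T > 5 and B > 3, so the Hy's law limits are exceeded at all 3,900 points. The Hy's law stop therefore decides every such case without cholestasis and without another cause.
2. Section 6.2 confines the guidelines to events judged related to tremelimumab, so the exception for another cause has little room. What remains is a drug-related case with cholestasis, for example T = 12 and B = 4 with raised alkaline phosphatase.
3. For that case, both rules withhold drug at once. Without recovery to Grade ≤1 or baseline within 14 days, both end in discontinuation. They part only if recovery occurs in that time and the taper, set at 28 days or more in the same row, is completed.

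**Check of the repair.** With 'and' in the hold rule (T ≤ 8 and B ≤ 5), the discontinue rule is its exact complement. Hold covers 600 points, discontinue covers 10,500 − 600 = 9,900, and the overlap is 0.

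**Grade 2 values.** T = 4 and B = 2.5 is Grade 2 on both analytes and exceeds the Hy's law limits. Those limits (>3 and >2) lie below the Grade 3 thresholds (>5 and >3), so a stop worded for any case necessarily reaches such a patient.

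**The case against.** The strongest reply is that a careful investigator would not be misled. Read analyte by analyte, ALT above 8 × ULN triggers its own discontinuation, and a milder bilirubin rule does not naturally cancel it. The General Considerations call for permanent discontinuation of dangerous Grade 3 events, the hepatitis row asks for a hepatology consult, Section 6.2 tells sites to consult the sponsor-investigator in case of doubt, and Section 11.1.3 presents the guidelines as an aid to clinical judgment. The unsettled patient must be drug-related, cholestatic, Grade 3 on both analytes, above exactly one cut-off and recovered within 14 days. In about 28 subjects this may never occur.

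Most of this stands and keeps the severity low. It does not remove the overlap. The General Considerations sentence depends on a judgment about the event. The advice to consult follows directly on the sentence about causality and helps only a site that notices the conflict. Section 6.3 leads back to the same table.

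Four stronger readings are tempting, and the documents do not support them.
- *The table tells one site to dose and another to stop.* Both rules withhold drug immediately; only later resumption differs.
- *The overlap also covers a single Grade 3 analyte*, such as ALT 10 with bilirubin 1.2 × ULN. Literally, bilirubin is then ≤5 × ULN. If the Grade 3 heading is taken to refer to the analyte that is Grade 3, only the discontinue rule applies.
- *The Grade 2 row permits re-dosing in Hy's law cases.* The stop covers any case, its limits reach Grade 2 values, and Section 6.3 directs such patients to Appendix 1. This is a matter of placement.
- *37% of Grade 3 patients are affected.* That figure describes the rule when both analytes are Grade 3, before the Hy's law stop is applied. Over all Grade 3 grid points (T 0.5 to 20, B 0.5 to 10; 17,620 points) the same overlap is 3,900 / 17,620 = 22%. Neither figure is a share of patients.

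**Conclusion.** Wrong as written, at low severity: an internally inconsistent dosing rule. With both analytes at Grade 3 and exactly one above its cut-off, the hold-and-resume rule and the discontinue rule both apply, and the cell gives no order between them. After the Hy's law stop, the unsettled case is a drug-related, cholestatic one. The disagreement there is confined to resumption after recovery within 14 days and a completed taper, unless the event is judged dangerous enough for the General Considerations to require a permanent stop.

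The conclusion rests on the printed 'or' in both rules and on Appendix 1 applying only to events judged related to tremelimumab. The documents give no rate of combined liver-test elevations, so the number of patients affected is unknown. The Simon design, the endpoints and the Section 12.7 toxicity rule are unaffected: that rule counts treatment-related Grade ≥3 events, and a patient in the overlap already has one.

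**What to change.** In the Grade 3 hepatitis cell, change the hold rule to transaminases ≤8 × ULN **and** bilirubin ≤5 × ULN, so that exceeding either limit means discontinue. This fits Section 3.1, which admits patients with a prior Grade 3 AST/ALT elevation only below eightfold and excludes prior Hy's law cases.

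As an optional clarification, repeat the Hy's law stop in the hepatitis Any Grade row and state that it overrides the grade rows. The slightly wider limits in Section 6.3 can stay as the trigger for referral to Appendix 1.

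The cost is a wording change in Appendix 1, with no added tests and no change to sample size, endpoints or stopping rules. Section 11.1.3 says that the Funder prepared the guidelines, so it would be sensible to agree the change with the Funder, though the documents do not say that this is required.

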**For Grade 4:**

Permanently discontinue study drug/study regimen.

| Nephritis or renal dysfunction | Any Grade              | General Guidance    | For Any Grade:   |
|--------------------------------|------------------------|---------------------|--|
| (elevated serum creatinine)    |                        |                     | 
 
– Consult with nephrologist.
 
– Monitor for signs and symptoms that may be related to changes in renal function (e.g., routine urinalysis, elevated serum BUN and creatinine, decreased creatinine clearance, electrolyte imbalance, decrease in urine output, or proteinuria).
 
– Patients should be thoroughly evaluated to rule out any alternative etiology (e.g., disease progression or infections).
 
– Steroids should be considered in the absence of clear alternative etiology even for low-grade events (Grade 2), in order to prevent potential progression to higher grade event.
 
 |
| Grade 1                 | No dose modifications. | For Grade 1: | 
 
– Monitor serum creatinine weekly and any accompanying symptoms. 
 
• If creatinine returns to baseline, resume its regular monitoring per study protocol.
 
• If creatinine worsens, depending on the severity, treat as Grade 2, 3, or 4.
 
 
 
– Consider symptomatic treatment, including hydration, electrolyte replacement, and diuretics.
 
   |

|   |  |   |
|---|--|---|
| Grade 2
(serum creatinine $>1.5$ to $3.0 \times$ baseline; $>1.5$ to $3.0 \times$ ULN)  | Hold study drug/study regimen until resolution to Grade $\leq 1$ or baseline. 
 
• If toxicity worsens, then treat as Grade 3 or 4.
 
• If toxicity improves to Grade <math>\leq 1</math> or baseline, then resume study drug/study regimen after completion of steroid taper.
 
 | For Grade 2: 
 
– Consider symptomatic treatment, including hydration, electrolyte replacement, and diuretics.
 
– Carefully monitor serum creatinine every 2 to 3 days and as clinically warranted.
 
– Consult nephrologist and consider renal biopsy if clinically indicated.
 
– If event is persistent (<math>>3</math> to 5 days) or worsens, promptly start prednisone 1 to 2 mg/kg/day PO or IV equivalent.
 
– If event is not responsive within 3 to 5 days or worsens despite prednisone at 1 to 2 mg/kg/day PO or IV equivalent, additional workup should be considered and prompt treatment with IV methylprednisolone at 2 to 4 mg/kg/day started.
 
– Once the patient is improving, gradually taper steroids over <math>\geq 28</math> days and consider prophylactic antibiotics, antifungals, and anti-PJP treatment (refer to current NCCN guidelines for treatment of cancer-related infections [Category 2B recommendation]).a
 
– When event returns to baseline, resume study drug/study regimen and routine serum creatinine monitoring per study protocol.
 
 |
| Grade 3 or 4
(Grade 3: serum creatinine $>3.0 \times$ baseline; $>3.0$ to $6.0 \times$ ULN;

Grade 4: serum creatinine $>6.0 \times$ ULN) | Permanently discontinue study drug/study regimen.  | For Grade 3 or 4: 
 
– Carefully monitor serum creatinine on daily basis.
 
– Consult nephrologist and consider renal biopsy if clinically indicated.
 
– Promptly start prednisone 1 to 2 mg/kg/day PO or IV equivalent.
 
– If event is not responsive within 3 to 5 days or worsens despite prednisone at 1 to 2 mg/kg/day PO or IV equivalent, additional workup should be considered and prompt treatment with IV methylprednisolone 2 to 4 mg/kg/day started.
 
– Once the patient is improving, gradually taper steroids over <math>\geq 28</math> days and consider prophylactic antibiotics, antifungals, and anti-PJP treatment (refer to current NCCN guidelines for treatment of cancer-related infections [Category 2B recommendation]).a
 
   |

| Rash | Any Grade
(excluding bullous skin formations) | General Guidance
(refer to NCI CTCAE v 4.03 for definition of severity/grade depending on type of skin rash)  | For Any Grade:
- Monitor for signs and symptoms of dermatitis (rash and pruritus).
- IF THERE IS ANY BULLOUS FORMATION, THE STUDY PHYSICIAN SHOULD BE CONTACTED AND STUDY DRUG DISCONTINUED.  |
|------|--|--|---|
|      | Grade 1                                   | No dose modifications.   | For Grade 1:
- Consider symptomatic treatment, including oral antipruritics (e.g., diphenhydramine or hydroxyzine) and topical therapy (e.g., urea cream).  |
|      | Grade 2                                   | For persistent (>1 to 2 weeks) Grade 2 events, hold scheduled study drug/study regimen until resolution to Grade $\leq 1$ or baseline.
• If toxicity worsens, then treat as Grade 3.
• If toxicity improves to Grade $\leq 1$ or baseline, then resume drug/study regimen after completion of steroid taper. | For Grade 2:
- Obtain dermatology consult.
- Consider symptomatic treatment, including oral antipruritics (e.g., diphenhydramine or hydroxyzine) and topical therapy (e.g., urea cream).
- Consider moderate-strength topical steroid.
- If no improvement of rash/skin lesions occurs within 3 to 5 days or is worsening despite symptomatic treatment and/or use of moderate strength topical steroid, consider, as necessary, discussing with study physician and promptly start systemic steroids such as prednisone 1 to 2 mg/kg/day PO or IV equivalent.
- Consider skin biopsy if the event is persistent for >1 to 2 weeks or recurs. |
|      | Grade 3 or 4                              | For Grade 3:
Hold study drug/study regimen until resolution to Grade $\leq 1$ or baseline.
If temporarily holding the study drug/study regimen does not provide improvement of the Grade 3 skin rash to Grade $\leq 1$ or baseline within 30 days, then permanently                                   | For Grade 3 or 4:
- Consult dermatology.
- Promptly initiate empiric IV methylprednisolone 1 to 4 mg/kg/day or equivalent.
- Consider hospitalization.
- Monitor extent of rash [Rule of Nines].
- Consider skin biopsy (preferably more than 1) as clinically feasible.
- Once the patient is improving, gradually taper steroids over $\geq 28$ days and consider prophylactic antibiotics, antifungals, and anti-PJP treatment (refer to current NCCN guidelines for  |

|  |   |                                       |   |
|--|---|---------------------------------------|---|
|  |   | discontinue study drug/study regimen. | 
 
treatment of cancer-related infections [Category 2B recommendation]).a
 
– Consider, as necessary, discussing with study physician.
 
   |
| For Grade 4:  |   |                                       |   |
| Permanently discontinue study drug/study regimen.  |   |                                       |   |
| Endocrinopathy

(e.g., hyperthyroidism, hypothyroidism, Type 1 diabetes mellitus, hypophysitis, hypopituitarism, and adrenal insufficiency; exocrine event of amylase/lipase increased also included in this section) | Any Grade

(depending on the type of endocrinopathy, refer to NCI CTCAE v4.03 for defining the CTC grade/severity) | General Guidance               | For Any Grade: 
 
– Consider consulting an endocrinologist for endocrine events.
 
– Consider, as necessary, discussing with study physician.
 
– Monitor patients for signs and symptoms of endocrinopathies. Non-specific symptoms include headache, fatigue, behavior changes, changed mental status, vertigo, abdominal pain, unusual bowel habits, polydipsia, polyuria, hypotension, and weakness.
 
– Patients should be thoroughly evaluated to rule out any alternative etiology (e.g., disease progression including brain metastases, or infections).
 
– Depending on the suspected endocrinopathy, monitor and evaluate thyroid function tests: TSH, free T3 and free T4 and other relevant endocrine and related labs (e.g., blood glucose and ketone levels, HgA1c).
 
– For modest asymptomatic elevations in serum amylase and lipase, corticosteroid treatment is not indicated as long as there are no other signs or symptoms of pancreatic inflammation.
 
– If a patient experiences an AE that is thought to be possibly of autoimmune nature (e.g., thyroiditis, pancreatitis, hypophysitis, or diabetes insipidus), the investigator should send a blood sample for appropriate autoimmune antibody testing.
 
 |
| Grade 1   | No dose modifications.  |                                       | For Grade 1 (including those with asymptomatic TSH elevation): 
 
– Monitor patient with appropriate endocrine function tests.
 
– For suspected hypophysitis/hypopituitarism, consider consultation of an endocrinologist to guide assessment of early-morning ACTH, cortisol, TSH and free T4; also consider gonadotropins, sex hormones, and prolactin levels, as well as
 
   |

|                     |   |   |
|---------------------|---|---|
|                     |   | 
cosyntropin stimulation test (though it may not be useful in diagnosing early secondary adrenal insufficiency).
 
 
– If TSH <math>< 0.5 \times</math> LLN, or TSH <math>> 2 \times</math> ULN, or consistently out of range in 2 subsequent measurements, include free T4 at subsequent cycles as clinically indicated and consider consultation of an endocrinologist.
 
   |
| Grade 2      | 
For Grade 2 endocrinopathy other than hypothyroidism and Type 1 diabetes mellitus, hold study drug/study regimen dose until patient is clinically stable.
 
 
• If toxicity worsens, then treat as Grade 3 or Grade 4.
 
 
Study drug/study regimen can be resumed once event stabilizes and after completion of steroid taper.
 
Patients with endocrinopathies who may require prolonged or continued steroid replacement (e.g., adrenal insufficiency) can be retreated with study drug/study regimen on the following conditions:
 
 
1. The event stabilizes and is controlled.
 
2. The patient is clinically stable as per investigator or treating physician's clinical judgement.
 
3. Doses of prednisone are <math>\leq 10</math> mg/day or equivalent.
 
 | 
For Grade 2 (including those with symptomatic endocrinopathy):
 
 
– Consult endocrinologist to guide evaluation of endocrine function and, as indicated by suspected endocrinopathy and as clinically indicated, consider pituitary scan.
 
– For all patients with abnormal endocrine work up, except those with isolated hypothyroidism or Type 1 DM, and as guided by an endocrinologist, consider short-term corticosteroids (e.g., 1 to 2 mg/kg/day methylprednisolone or IV equivalent) and prompt initiation of treatment with relevant hormone replacement (e.g., hydrocortisone, sex hormones).
 
– Isolated hypothyroidism may be treated with replacement therapy, without study drug/study regimen interruption, and without corticosteroids.
 
– Isolated Type 1 diabetes mellitus (DM) may be treated with appropriate diabetic therapy, without study drug/study regimen interruption, and without corticosteroids.
 
– Once patients on steroids are improving, gradually taper immunosuppressive steroids (as appropriate and with guidance of endocrinologist) over <math>\geq 28</math> days and consider prophylactic antibiotics, antifungals, and anti-PJP treatment (refer to current NCCN guidelines for treatment of cancer-related infections [Category 2B recommendation]).a
 
– For patients with normal endocrine workup (laboratory assessment or MRI scans), repeat laboratory assessments/MRI as clinically indicated.
 
 |
| Grade 3 or 4 | 
For Grade 3 or 4 endocrinopathy other than hypothyroidism and Type 1 diabetes mellitus, hold
   | 
For Grade 3 or 4:
 
 
– Consult endocrinologist to guide evaluation of endocrine function and, as indicated by suspected endocrinopathy and as
 
  |

|   |  |  |  |
|---|--|--|--|
|   |  | 
study drug/study regimen dose until endocrinopathy symptom(s) are controlled.
 
Study drug/study regimen can be resumed once event stabilizes and after completion of steroid taper.
 
Patients with endocrinopathies who may require prolonged or continued steroid replacement (e.g., adrenal insufficiency) can be retreated with study drug/study regimen on the following conditions:
 
 
1. The event stabilizes and is controlled.
 
2. The patient is clinically stable as per investigator or treating physician's clinical judgement.
 
3. Doses of prednisone are <math>\leq 10</math> mg/day or equivalent.
 
 | 
clinically indicated, consider pituitary scan. Hospitalization recommended.
 
 
– For all patients with abnormal endocrine work up, except those with isolated hypothyroidism or Type 1 DM, and as guided by an endocrinologist, promptly initiate empiric IV methylprednisolone 1 to 2 mg/kg/day or equivalent, as well as relevant hormone replacement (e.g., hydrocortisone, sex hormones).
 
– For adrenal crisis, severe dehydration, hypotension, or shock, immediately initiate IV corticosteroids with mineralocorticoid activity.
 
– Isolated hypothyroidism may be treated with replacement therapy, without study drug/study regimen interruption, and without corticosteroids.
 
– Isolated Type 1 diabetes mellitus may be treated with appropriate diabetic therapy, without study drug/study regimen interruption, and without corticosteroids.
 
– Once patients on steroids are improving, gradually taper immunosuppressive steroids (as appropriate and with guidance of endocrinologist) over <math>\geq 28</math> days and consider prophylactic antibiotics, antifungals, and anti-PJP treatment (refer to current NCCN guidelines for treatment of cancer-related infections [Category 2B recommendation]).a
 
 |
| Neurotoxicity

(to include but not be limited to limbic encephalitis and autonomic neuropathy, excluding Myasthenia Gravis and Guillain-Barre) | Any Grade

(depending on the type of neurotoxicity, refer to NCI CTCAE v4.03 for defining the CTC grade/severity) | General Guidance  | For Any Grade:

 
– Patients should be evaluated to rule out any alternative etiology (e.g., disease progression, infections, metabolic syndromes, or medications).
 
– Monitor patient for general symptoms (headache, nausea, vertigo, behavior change, or weakness).
 
– Consider appropriate diagnostic testing (e.g., electromyogram and nerve conduction investigations).
 
– Perform symptomatic treatment with neurological consult as appropriate.
 
  |

|                     |  |  |
|---------------------|--|--|
| Grade 1      | No dose modifications.   | For Grade 1:
– See “Any Grade” recommendations above.  |
| Grade 2      | 
For acute motor neuropathies or neurotoxicity, hold study drug/study regimen dose until resolution to Grade <math>\leq 1</math>.
 
For sensory neuropathy/neuropathic pain, consider holding study drug/study regimen dose until resolution to Grade <math>\leq 1</math>.
 
If toxicity worsens, then treat as Grade 3 or 4.
 
Study drug/study regimen can be resumed once event improves to Grade <math>\leq 1</math> and after completion of steroid taper.
 | For Grade 2:
– Consider, as necessary, discussing with the study physician.
– Obtain neurology consult.
– Sensory neuropathy/neuropathic pain may be managed by appropriate medications (e.g., gabapentin or duloxetine).
– Promptly start systemic steroids prednisone 1 to 2 mg/kg/day PO or IV equivalent.
– If no improvement within 3 to 5 days despite 1 to 2 mg/kg/day prednisone PO or IV equivalent, consider additional workup and promptly treat with additional immunosuppressive therapy (e.g., IV IG). |
| Grade 3 or 4 | 
For Grade 3:
 
Hold study drug/study regimen dose until resolution to Grade <math>\leq 1</math>.
 
Permanently discontinue study drug/study regimen if Grade 3 imAE does not resolve to Grade <math>\leq 1</math> within 30 days.
 
For Grade 4:
 
Permanently discontinue study drug/study regimen.
  | For Grade 3 or 4:
– Consider, as necessary, discussing with study physician.
– Obtain neurology consult.
– Consider hospitalization.
– Promptly initiate empiric IV methylprednisolone 1 to 2 mg/kg/day or equivalent.
– If no improvement within 3 to 5 days despite IV corticosteroids, consider additional workup and promptly treat with additional immunosuppressants (e.g., IV IG).
– Once stable, gradually taper steroids over $\geq 28$ days.  |

| Peripheral neuromotor syndromes
(such as Guillain-Barre and myasthenia gravis) | Any Grade      | General Guidance  | For Any Grade:   |
|---|----------------|---|--|
